#### 7.2. Laboratory Evaluations

Summaries of laboratory data will be provided for the Safety Analysis Set and will include data collected up to the date of last dose of any study drug plus 30 days for subjects who have permanently discontinued study drug. The analysis will be based on values reported in conventional units. When values are below the LOQ, they will be listed as such, and the imputed value will be used for the purpose of calculating summary statistics as specified in Section 3.7.

A by-subject listing for laboratory test results will be provided by subject ID and analysis visit in chronological order for screening tests, hematology, serum chemistry, and coagulation, separately. Values falling outside of the relevant reference range and/or having a severity grade of 1 or higher according to CTCAE toxicity grading will be flagged in the data listings, as appropriate.

No formal statistical testing is planned.

#### Special handling of central laboratory serum creatinine data:

At initiation of the study, the Covance Statement of Work (SOW) specified that serum creatinine be analyzed using the Jaffe method with a reflex to serum enzymatic creatinine. Early in the

study, high bilirubin values prohibited resulting of creatinine, so the SOW was updated to use serum enzymatic creatinine with a reflex to LCMSMS methodology if serum enzymatic creatinine could not be resulted; Jaffe method was no longer used. At the same time, Gilead asked Covance to perform regression analysis to determine if data from serum enzymatic creatinine and LCMSMS methods were combinable. Fourty samples (not from this study) measured creatinine using all 3 methods (Jaffe, enzymatic serum creatinine, and LCMSMS), and regression analysis using Deming and regular regression was performed.

Results of previous regression analyses comparing the Jaffe method and serum enzymatic creatinine met Covance's criteria for combinability of data using the 2 methods (ie, 95% CI on slope contains 1; and 95% CI on intercept contains 0). Regression analysis of the 40 samples for LCMSMS and the Jaffe methods came close to meeting the combinability criteria, and only 4 samples from Study GS-US-416-2124 were analyzed using the Jaffe method. LCMSMS and serum enzymatic creatinine failed to pass the combinability criteria (95% CI on the slope contained 1; but 95% CI on the intercept did not contain 0). Examination of individual data points as well as the reported bias (-0.055 mg/dL) show that serum LCMSMS was reading out approximately .055 mg/dL lower than serum enzymatic creatinine across the range of values.

In order to combine creatinine data from the 3 different test methods, Gilead will create a new lab test code called "GSI Serum Creatinine" that combines data from the 3 serum creatinine methods for analysis---adjusting for the LCMSMS negative bias (by adding 0.06 mg/dL [for 2-decimal place reporting] to the reported result). Covance has recommended using Jaffe normal ranges for serum creatinine LCMSMS, and results from prior regression analysis suggest that serum enzymatic creatinine is combinable with the Jaffe method. Results of the "GSI serum creatinine" lab test code will be toxicity graded using CTCAE Version 4.03 and the Jaffe method normal ranges.

## 7.2.1. Summaries of Numeric Laboratory Results

Descriptive statistics will be provided by treatment group for hemoglobin, hematocrit, lymphocytes, neutrophils, platelet count, white blood cells (WBCs), bicarbonate, sodium, chloride, magnesium, phosphorus, potassium, albumin-corrected calcium, lactate dehydrogenase, blood urea nitrogen, serum creatinine, and serum glucose as follows:

- Baseline values
- Values at each postbaseline analysis visit
- Change from baseline at each postbaseline analysis visit

A baseline laboratory value will be defined as the last measurement obtained on or prior to the date of first dose of study drug. Change from baseline to a postbaseline visit will be defined as the value at the visit minus the baseline value. The mean, SD, median, Q1, Q3, minimum, and maximum values will be displayed to the reported number of digits; SD values will be displayed to the reported number of digits plus 1.

Median (Q1, Q3) serum creatinine value over time will be plotted.

In the case of multiple values in an analysis window, data will be selected for analysis as described in Section 3.8.3.

## 7.2.2. Graded Laboratory Values

The CTCAE Version 4.03 will be used for assigning toxicity grades (0 to 4) to laboratory results for analysis. Grade 0 includes all values that do not meet the criteria for an abnormality of at least Grade 1. For laboratory tests with criteria for both increased and decreased levels, analyses for each direction (ie, increased, decreased) will be presented separately.

#### 7.2.2.1. Treatment-Emergent Laboratory Abnormalities

Treatment-emergent laboratory abnormalities are defined as values that increase at least 1 toxicity grade from baseline at any postbaseline time point, up to and including the date of last dose of study drug plus 30 days for subjects who permanently discontinued study drug. If the relevant baseline laboratory value is missing, any abnormality of at least Grade 1 observed within the time frame specified above will be considered treatment emergent.

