8.4. Data Handling Conventions

Missing data can have an impact on the interpretation of the trial data. In general, values for missing data will not be imputed.

Where appropriate, safety data for subjects who received study drug but did not complete the study will be included in summary statistics. For example, if a subject received study medication, the subject will be included in a summary of adverse events according to the treatment received; however, if the subject is not dosed then they will be excluded from the summary. If safety laboratory results for a subject are missing for any reason at a time point, the subject will be excluded from the calculation of summary statistics for that time point. If the subject is missing a predose value, then the subject will be excluded from the calculation of summary statistics for the predose value and the change from predose values.

Values for missing safety laboratory data, ECGs, and vital signs will not be imputed; however, a missing baseline result will be replaced with a Screening result, if available. If no pre-treatment laboratory value is available, the baseline value will be assumed to be normal (ie, no grade [Grade 0]) for the summary of graded laboratory abnormalities.

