8.8.3. Laboratory Evaluations

Selected laboratory data (using conventional units) will be summarized using only observed data. The value and change from baseline at all scheduled time points will be summarized.

[figure not shown]
Graded laboratory abnormalities will be defined using the grading scheme in the CTCAE Version 4.03.

Incidence of treatment-emergent grade 3 or higher laboratory abnormalities, defined as most severe grade 3 or higher post-baseline value that has increased by at least one toxicity grade from baseline at any time post baseline up to 30 days after the last dose of study drug, will be summarized by treatment group. If baseline data are missing, then any graded abnormality (ie, at least a Grade 1) will be considered treatment emergent.

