#### 6.3. Exploratory Efficacy Endpoints

#### 6.5. Changes to Efficacy Analysis

Analyses of the endpoints change from baseline in LOXL2, CK18, serum cytokines and metabolic profiles, LPS, procalcitonin, and ASK-1 pathways will be described in a separate biomarker analysis plan (BAP).

Fasting lipid tests (total cholesterol, HDL, LDL, VLDL), and triglycerides will not be summarized as exploratory efficacy endpoints as the requirement for fasting was removed in Amendment 2 of the protocol. In addition, Covance laboratories does not report results for cholesterol values when the sample is "icteric". As a high percentage of subjects have total bilirubin levels > 10 mg/dL for this subject population, these analyses would exclude the most severe AH subjects, and would not be representative of the entire set of subjects. The lipid profile will be summarized for safety only and insulin levels will be listed only using the same visit windows used for HbA1c.

It should also be noted that many GGT and total protein values were cancelled by Covance due to icteric samples (ie, high total bilirubin). Summaries will be presented for completeness, but it should be noted that many values, especially those at early timepoints, will be missing.

Analysis of the Chronic Liver Disease Questionnaire (CLDQ) will not be performed for the final analysis since there was no evidence of improved efficacy with treatment of SEL + PRED vs. PLA + PRED when the primary analysis was performed.

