#### 7.2.2.2. Treatment-Emergent Marked Laboratory Abnormalities

Treatment-emergent marked laboratory abnormalities are defined as values that increase from baseline by at least 3 toxicity grades at any postbaseline time point, up to and including the date of the last dose of study drug plus 30 days for subjects who permanently discontinued study drug. If the relevant baseline laboratory value is missing, any Grade 3 or 4 values observed within the timeframe specified above will be considered treatment-emergent marked abnormalities.

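### For tests lost to icterus, chiefly GGT, treating a missing baseline as Grade 0 can count abnormalities present at entry as treatment-emergent

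*SAP*

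**What the plan says.** **The rule.** Protocol 8.4 first looks for an earlier value: "a missing baseline result will be replaced with a Screening result, if available". If there is no pre-treatment value at all, "the baseline value will be assumed to be normal (ie, no grade [Grade 0]) for the summary of graded laboratory abnormalities". Protocol 8.8.3 states the consequence: "If baseline data are missing, then any graded abnormality (ie, at least a Grade 1) will be considered treatment emergent". SAP 7.2.2.1 repeats it ("If the relevant baseline laboratory value is missing, any abnormality of at least Grade 1 observed within the time frame specified above" is treatment-emergent). SAP 7.2.2.2 extends it to the marked table, where "any Grade 3 or 4 values observed within the timeframe specified above will be considered treatment-emergent marked abnormalities". Under SAP 7.2.2.3 the denominator needs only a postbaseline value, so a subject with no baseline enters both tables.

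**Why baselines are missing.** SAP 6.5 says that "many GGT and total protein values were cancelled by Covance due to icteric samples", and that the gaps are concentrated at early visits. It adds that the central laboratory does not report cholesterol in icteric samples and that a high percentage of subjects have bilirubin above 10 mg/dL. The SAP's note on creatinine says that early in the study "high bilirubin values prohibited resulting of creatinine", after which the assay was changed.

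**Which laboratory counts.** SAP 1.2 bases all efficacy and safety laboratory analyses on central results. The only local-data exceptions are for Lille and MELD (SAP 3.6.1).

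**The concern.** Setting a missing baseline to Grade 0 is a reasonable default when the gap says nothing about the patient. Here, for the named tests, the gap is caused by the disease. A subject can enter with a GGT that is abnormal but cannot be measured, become less jaundiced on treatment, and then have a GGT reported. If that value is Grade 3 or 4, the plan tabulates it as emergent and as marked, although it may be no worse than at entry.

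The Screening fallback is unlikely to help much. That sample is taken within 14 days before randomization (Protocol 6.2.1), usually from the same jaundiced patient.

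Laboratory tests are part of the primary safety endpoint (Protocol 8.1.1). Grade 3 and higher treatment-emergent laboratory abnormalities are also among the items the DMC monitors (Protocol 8.11). A rate that mixes new events with unmeasured old ones is hard to interpret in either arm. It is also not guaranteed to be equally wrong in both, because a false event requires bilirubin to fall.

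**Working it through.** The documents give no figure for this point, so there is nothing to reproduce. The check has two parts: which tests the rule can affect, and how large the effect could be.

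**1. Tests affected**

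- *GGT.* Icteric loss is documented (SAP 6.5). SAP 3.8.2 says that laboratory parameters serving both efficacy and safety, such as hepatic synthetic function tests, have toxicity-grading summaries. The note to Table 3-1 lists GGT among those tests. GGT is in the chemistry panel at every visit, so a later result has many chances to appear.
- *Cholesterol.* Icteric loss is documented, and SAP 6.5 keeps lipids for safety only. Grading under CTCAE 4.03 is assumed. After baseline, lipids are scheduled at Weeks 4, 12 and 24. With a last dose on Day 28 the safety window closes on Day 28 + 30 = Day 58, before Week 12 (Day 84), so only the Week 4 sample counts.
- *Total protein.* Icteric loss is documented. The documents do not show whether it is graded.
- *Creatinine.* Loss is documented only early in the study. The method was changed, and entry excludes values above 2.5 mg/dL (Protocol 4.3), so a severe abnormality at entry is less likely. Weak.
- *ALT, AST, bilirubin, INR, electrolytes, hematology.* No icteric loss is documented.

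The marked table is more exposed than the Grade 3/4 table. With an observed baseline, a rise from Grade 1 or 2 to Grade 3 is less than three grades and is not marked. With a missing baseline it is.

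**2. Illustration for one affected test (Grade 3/4 table)**

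Inputs, all assumed except n:
- n = 60 per arm, the upper end of the planned 50-60 (SAP 1.2)
- m = share with baseline lost to icterus
- r = share of those with a later result
- q = share of those already Grade 3-4 at entry, still so and not worse at the later value
- t = true emergent rate

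Formulas:
- False events per arm = n × m × r × q
- Reported rate = [(1−m)t + m r (q + (1−q)t)] / [(1−m) + m r]

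Mid case, m = 0.30, q = 0.30, r = 0.60, t = 0.05:
- False events: 60 × 0.30 × 0.60 × 0.30 = 3.2
- Numerator: 0.70 × 0.05 + 0.18 × (0.30 + 0.70 × 0.05) = 0.0350 + 0.0603 = 0.0953
- Denominator: 0.70 + 0.18 = 0.88
- Reported rate: 0.0953 / 0.88 = 10.8%, against a true 5% (with t = 0 it is 6.1%)

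Range, m = 10-50%, q = 10-50%, r = 30-90%: 0.2 to 13.5 false events per arm. The reported rate runs from 0.3% to 23.7% when t = 0, and from 5.3% to 27.5% when t = 5%.

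Unequal clearance, same m, q and t, with r = 0.80 in one arm and 0.50 in the other:
- 0.1154 / 0.94 = 12.3%
- 0.08525 / 0.85 = 10.0%
- Difference 2.2 points before rounding, with no true difference; false events 4.3 against 2.7

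**3. What a split would show in the mid case**

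- Observed baseline: 42 subjects, 42 × 0.05 = 2.1 events, 5.0%
- Baseline not measurable, later resulted: 60 × 0.18 = 10.8 subjects, 10.8 × 0.335 = 3.6 events, 33.5%

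The observed-baseline row recovers t for any m, q and r, provided the true rate is the same in subjects with and without a measurable baseline.

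**The case against.** The other side has several good arguments.

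- **Narrow scope.** A reader might infer that baselines across the panel are missing because of jaundice, or that the drug's liver-safety picture is compromised. The documents do not support that. The trial and individual laboratory stopping criteria use ALT, AST and bilirubin (Protocol 8.11, SAP 7.1.7), for which no icteric loss is described. This stands.
- **Conditional direction.** A reader might infer that an effective drug would look more toxic. That needs faster bilirubin clearance in one arm, which no document shows. SAP 6.5 reports no evidence of improved efficacy at the primary analysis. Even the 80% against 50% imbalance above moves the comparison by only about 2 points. This stands; inflation in both arms does not depend on it.
- **Unknown size.** No missingness share, baseline GGT or grade distribution is given, so every percentage above is an assumption. That GGT was abnormal at entry is a reasonable inference in severe AH, not a stated fact. This stands.
- **Over-counting is cautious, and cases can be traced.** The tables are descriptive, SAP 6.5 warns that early GGT is missing, and the Grade 3/4 listing shows all results for the test. This stands in part: a reader can find the cases in the listing, but the tables do not separate them.
- **Replacing the rule now would be worse.** The rule is in the protocol, treatment was unblinded for the primary analysis (SAP 2.3), and SAP 7.7 declares no departures from the protocol's safety analyses. Dropping subjects with no baseline removes the most jaundiced, and SAP 6.5 gave a similar reason for not summarizing lipids as efficacy endpoints. This stands, and it rules out replacing the tables.

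**Conclusion.** The point holds for the tests the SAP itself says were lost to icterus: GGT first, cholesterol second, total protein only if it is graded, and some early creatinines as a weak case. For these, the plan can tabulate abnormalities present at entry as treatment-emergent Grade 3/4 or marked, in both arms. The effect would be larger in an arm whose bilirubin cleared faster.

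The rule, the cause of the missingness and the denominator are documented. The size is not: the move from 5% to 10.8% is an illustration on assumed inputs. The conclusion rests on two further assumptions: that a material share of subjects had neither a Screening nor a Day 1 central result for the test, and that some of them were already Grade 3 or 4. The documents do not support extending it to the rest of the laboratory panel, or claiming an actual between-arm distortion in this trial.

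**What to change.** Keep the protocol-specified tables and add to them.

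1. In SAP 7.2.2.3, for GGT, cholesterol, creatinine and (if graded) total protein, show by arm the events in subjects whose Screening and Day 1 central values were both cancelled or not reported. Label the line 'baseline not measurable, icteric' and give its denominator.
2. Add a supplementary version of the Grade 3/4 and marked tables that requires an observed baseline in both numerator and denominator.
3. Use local pre-treatment values only as a sensitivity analysis, and only where recorded. Local Screening creatinine is on the SAP 4.3 list. Local GGT is drawn (Protocol 6.2.1) but is not on that list. The Screening lipid profile goes to the central laboratory only.
4. Declare the addition in SAP 7.7 as made after the primary-analysis unblinding.

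The cost is one programming flag, a few rows and two supplementary tables. The supplementary version has a smaller and less jaundiced denominator, so it should be read beside the main tables and not in place of them.

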#### 7.2.2.2. Treatment-Emergent Marked Laboratory Abnormalities

Treatment-emergent marked laboratory abnormalities are defined as values that increase from baseline by at least 3 toxicity grades at any postbaseline time point, up to and including the date of the last dose of study drug plus 30 days for subjects who permanently discontinued study drug. If the relevant baseline laboratory value is missing, any Grade 3 or 4 values observed within the timeframe specified above will be considered treatment-emergent marked abnormalities.

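### The marked-abnormality table cannot count a subject who starts at Grade 2 or above on a test, yet keeps that subject in its denominator; baseline-relative liver tables would close the gap cheaply

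*SAP*

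**What the plan says.** SAP 7.2.2 states that CTCAE Version 4.03 "will be used for assigning toxicity grades (0 to 4) to laboratory results", with increases and decreases analysed separately. Two graded summaries follow, both described in SAP 7.2.2.3.

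- **Table 15.11.6.2, treatment-emergent Grade 3 or 4.** Treatment-emergent means "values that increase at least 1 toxicity grade from baseline at any postbaseline time point" (SAP 7.2.2.1). This matches Protocol 8.8.3, which asks for the "most severe grade 3 or higher post-baseline value that has increased by at least one toxicity grade from baseline".
- **Table 15.11.6.3, marked abnormalities.** Marked means "values that increase from baseline by at least 3 toxicity grades at any postbaseline time point" (SAP 7.2.2.2). There is a separate rule for an absent baseline: "If the relevant baseline laboratory value is missing, any Grade 3 or 4 values observed within the timeframe specified above" count as marked. Protocol 8.8.3 has no marked category, so this table is an addition made by the SAP.

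The denominator for both is everyone with a postbaseline result in the window that ends 30 days after the last dose. Subjects whose baseline grade rules out the event are not removed.

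**The concern.** The trial enrols people whose liver tests are already abnormal. Protocol 4.2 requires recent jaundice, a Maddrey's DF of at least 32 and an AST of at least 50 U/L. SAP 6.5 remarks that "a high percentage of subjects have total bilirubin levels > 10 mg/dL for this subject population". A rule that needs room for a three-grade rise has least room on the tests where liver injury from the study drug would be looked for.

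Safety is the primary endpoint (Protocol 8.1.1) and laboratory tests are part of it. A table labelled as marked abnormalities, with low counts for bilirubin or INR and no footnote, could be taken as reassurance when part of the explanation is that some subjects could not have had the event.

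**Working it through.** No figure in the plan needs to be reproduced. The check is to list every pair of baseline and postbaseline grades and apply both rules.

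**Inputs.** Scale 0 to 4 (SAP 7.2.2). Marked: postbaseline minus baseline at least 3 (SAP 7.2.2.2). Grade 3 or 4 table: postbaseline at least 3 and a rise of at least 1 (SAP 7.2.2.1 and 7.2.2.3).

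| Baseline grade | Largest possible rise (4 − baseline) | Postbaseline grades counted as marked | Postbaseline grades counted in the Grade 3 or 4 table |
|---|---|---|---|
| 0 | 4 | 3, 4 | 3, 4 |
| 1 | 3 | 4 | 3, 4 |
| 2 | 2 | none | 3, 4 |
| 3 | 1 | none | 4 |
| 4 | 0 | none | none |
| missing | not defined | 3, 4 | 3, 4 |

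Seven worsenings end in Grade 3 or 4: 0→3, 0→4, 1→3, 1→4, 2→3, 2→4 and 3→4. The marked rule counts three of them (0→3, 0→4, 1→4). The Grade 3 or 4 table counts all seven. Only a baseline of Grade 4 is missed by both tables.

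A side effect is that a subject with no baseline counts as marked on reaching Grade 3, while a subject known to start at Grade 2 does not count even on reaching Grade 4.

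**Dilution of the marked percentage.** Let s be the share of subjects at Grade 2 or above at baseline on a test, and r the marked rate among those able to qualify. The table shows r × (1 − s). The documents do not give s, so these values are assumptions. With r = 10%:

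- s = 25%: 10% × 0.75 = 7.5%
- s = 50%: 10% × 0.50 = 5.0%
- s = 75%: 10% × 0.25 = 2.5%
- s = 100%: 0%

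**What else would show worsening from an abnormal baseline.**

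- SAP 7.2.1 (numeric safety tables) does not include ALT, AST, bilirubin or INR.
- SAP 6.2.8 gives value, change and percentage change for those tests through Week 24. These are efficacy tables on the FAS and mITT sets and leave out data after transplantation (SAP 6). They describe the distribution, not how many subjects passed a given multiple of baseline.
- SAP 7.1.7 reports confirmed ALT or AST above 5 times baseline, ALT or AST above 500 U/L, and confirmed bilirubin above 3 times baseline or nadir. Screening stops at the last selonsertib/placebo dose, apart from confirmatory values, whereas the graded tables run 30 days further. INR has no such criterion. Relative to baseline, the bilirubin criterion means more than 3 × 10 = 30 mg/dL from a start of 10, or more than 3 × 14 = 42 mg/dL from 14, the subgroup cut in SAP 3.4.
- Protocol 7.5.1 sends possible drug-induced liver injury to an independent hepatologist, including bilirubin above 2 times with ALT or AST above 3 times baseline or nadir. SAP Appendix 1 lists no table for that combination or for the adjudicated categories.

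**The case against.** The strongest reply is that the marked table is supplementary and that worsening from an abnormal baseline is visible elsewhere. Most of this stands. The protocol's own graded analysis counts 2→3, 2→4 and 3→4. Percentage change in INR and bilirubin is tabulated. The mITT set equals the Safety Analysis Set if every subject received the assigned treatment (SAP 3.1.2). Lille scores above 0.85, which reflect bilirubin change, are listed, and so are all liver chemistry and coagulation results. Laboratory safety is descriptive, with no testing (SAP 7.2).

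A reader might therefore go too far in three ways:

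- **That the primary safety tables cannot see liver toxicity.** They can. The limit belongs to one added table, and applies per test and direction, so the same subject can still be counted for other tests.
- **That the marked table must be near zero for bilirubin and INR.** The documents print neither the CTCAE cut-offs nor the laboratory reference ranges, so baseline grades cannot be derived. The remark about bilirubin above 10 mg/dL gives no share.
- **That the comparison between arms is biased.** The rule is the same in both randomised arms. A chance imbalance in baseline grade would move the crude percentages, but none is shown.

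The reply does not cover everything. No planned safety table shows worsening of bilirubin, INR, AST or ALT relative to baseline, as a count of subjects, over the full treatment-emergent window.

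**Conclusion.** The point holds as a limit of one supplementary table. For a given test and direction, a subject with a known baseline of Grade 2 or above cannot appear in Table 15.11.6.3 but stays in its denominator. A Grade 1 baseline can qualify only through Grade 4. Table 15.11.6.2 still counts worsening from Grades 0 to 3, so the blind spot shared by both graded tables is a baseline of Grade 4.

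The result about grades follows from the definitions and needs no assumption. The dilution figures (10% shown as anything from 7.5% to 0%) rest wholly on assumed shares.

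Relevance is greatest for bilirubin, INR and AST, which the entry criteria select to be abnormal. It is weaker for ALT, which has no entry floor: with the required AST/ALT ratio of at least 1.5, an AST of 50 U/L means an ALT of at most 50 / 1.5 = 33 U/L. The definition is not an error, and sample size, power and alpha are unaffected. This is a worthwhile, inexpensive improvement in a trial whose primary endpoint is safety.

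**What to change.** 1. On the Safety Analysis Set, through the last dose of any study drug plus 30 days, add a shift table of baseline grade by worst postbaseline grade for total bilirubin, INR, AST and ALT, by treatment group. It also shows how many subjects start at each grade, including Grade 4.
2. For the same tests, set and window, add the number and percentage of subjects in fold-from-baseline categories. The multiples already in Protocol 7.5.1 (2 and 3 for bilirubin, 3 and 5 for ALT and AST) could be reused, with INR multiples fixed in advance. These are descriptive only and change no stopping rule.
3. Keep Table 15.11.6.3 on its full denominator. Footnote that a known baseline of Grade 2 or above cannot qualify, and add the number and percentage among subjects able to qualify (baseline Grade 0, 1 or missing). Replacing the denominator would be a poor trade: with s = 75%, an arm of 50 to 60 would shrink to 0.25 × 50 = 12.5 to 0.25 × 60 = 15 subjects.

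The cost is a few extra descriptive tables from central laboratory data already collected. Treatment assignments were unblinded for the primary analysis (SAP 2.3), so the categories should be fixed before the tables are run and the tables labelled as added afterwards. If the SAP is already final, the change goes in the clinical study report, as SAP Section 1 provides.
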